One of the secondary objectives is to assess escape (Section 2.2). The definition of escape has been modified to include its relation to the highest tolerated dose of LCI699. The concept of escape refers to loss of control of UFC after having attained normalization of UFC on LCI699 therapy at an earlier time point. In this study, it is permitted to increase the dose of LCI699 not only during the dose titration phase (weeks 1-10), but also during the treatment period (weeks 11-22) of the core study, and during the extension study if applicable. This is intended to mimic clinical practice. The additional requirement to have uncontrolled UFC at the highest tolerated dose of LCI699 is also intended to reflect anticipated clinical use of the drug. The highest tolerated dose is the highest dose without a drug-suspected adverse event (AE), up to the maximum LCI699 dose of 30mg bid.

The requirement of uncontrolled UFC on two consecutive visits is intended to ensure that the elevated UFC is not due to lab error or variations just above the upper limit of the normal reference range. Escape events will be described by a Kaplan-Meier analysis of “time to escape,” i.e., the time (in weeks) from the first normalization of UFC to the first of two consecutive uncontrolled UFC levels (Section 9.5.2).

Changes to the protocol

Changes to specific sections of the protocol are shown in the track changes version of the protocol using ~~strike through red font for deletions~~ and red underlined for insertions.

Protocol synopsis: Edited to be consistent with changes throughout the protocol.

Assessment Schedules: Table has been updated to reflect the intensive cardiac monitoring (ECG and Holter) and the additional interim visits when dose escalation should occur if needed.

[figure not shown]
Section 1.1.1.1 (Table 1-1): Safety margin multiples for the 30 mg bid dose have been added to Table 1-1.

Section 1.1.1.4: This section has been updated to include estimation of PK exposure at 30 mg bid, and added background on emerging preclinical data regarding LCI699 metabolism.

Section 2.2: Secondary objective on escape, and the definition of escape, were modified.

Section 3.1: Addition of the interim dose escalation visits and update of Figure 3-1 to reflect new design with interim visits. Section updated (including Figure 3-1) to reflect the change of the maximum dose strength of 30 mg.

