At Day 154, patients have the option to enter the 12 month extension phase at the investigators discretion provided they do not meet any discontinuation criteria. Dosing titration during the extension is to be based on efficacy (UFC control) and safety ([Section 5.5.4](#)). Patients will come in for monthly visits for the first 6 months (Day 154- Day 322) of the long-term extension and then will have visits every 3 months from month 6 through 12 (Day 322 - Day 490). At the end of the extension phase, patients will complete an End of Treatment-Extension visit at Day 490 and an End of Study visit 28 days after the last dose administration, if not continuing into long term Extension-2.

Optional long term extension-2

At Day 490, patients have the option to enter a second long term extension phase (extension-2) at the investigator's discretion, provided they do not meet any of the study discontinuation criteria. Dose adjustment during the extension is to be based on efficacy (UFC control) and safety ([Section 5.5.4](#)). Patients will come in for visits every 3 months during the first 18 months of extension-2 (approximately 3 years into the study), and every 6 months thereafter. This additional long term extension (extension-2) will provide important long term safety and efficacy data of LCI699 in patients with Cushing's disease.

1. Patient treatment in Long Term Extension-2 will end at each site within 4 months after a separate roll-over study is opened at their site, or by 31 December 2019 (whichever occurs

earlier). The roll-over study will provide an opportunity of continued treatment for patients who are still ongoing at that time and who are clinically benefitting from LCI699. For sites where a separate roll-over study is not an option, the patient may be offered a local alternative treatment option.

Patients entering the roll-over protocol will complete an EOT visit. For these patients the EOS visit is not applicable, as treatment on LCI699 will not be interrupted. Sites with the separate roll-over study option available, should arrange their patient's End of Treatment (EOT) visit within 4 months of the roll-over study being opened at their site (i.e. earlier than the 6 month visit intervals in Long-Term Extension-2), to allow their patients to continue their LCI699 dose on this new study.

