3.5 Risk/ benefit for this study

Potential benefits

Biochemical remission is a goal in the treatment of Cushing's disease. Preliminary data from this PoC study in patients with Cushing's disease clearly demonstrated that LCI699 can reduce and normalize plasma cortisol in this population. However, it is unknown whether patients responding to LCI699 will eventually loose UFC control. Patients will be discontinued from LCI699 treatment in case of unsatisfactory response.

The primary treatment and standard of care for Cushing's disease is surgical removal of the pituitary tumor via transsphenoidal adenectomy. Therefore, in order to avoid any potential delay in receiving first line treatment patients enrolled under [Amendment 4](#) should have either failed standard therapy (including surgery) or can be de novo patients for whom surgery is not an option. Given LCI699's potency to suppress cortisol synthesis, it is conceivable that patients may ameliorate some of the sequelae of their hypercortisolism state while on the drug for the planned duration of this study protocol following [Amendment 4](#). Patients who are responding to LCI699 with good tolerability have the option to participate in optional two long term extension phases of the study.

Potential risks

Based on the preclinical and clinical experience with LCI699 the risks associated with this study are outlined below. The risks to patients will be minimized by strict inclusion/exclusion criteria, close clinical monitoring and predefined dose adjustment and dose termination criteria (see [Section 5.5.4](#) and [Section 5.5.9](#)).

Effects on QTc interval

Final results from the completed ICH E14-compliant thorough QT Study LCI699C2105 showed that the predicted mean QT effect of osilodrostat was below the threshold of regulatory concern for the currently investigated dose range (2-30 mg twice a day [bid]).

Effects on blood pressure

LCI699 has been shown to reduce BP of hypertensive patients in a dose dependent manner over 4-8 weeks. An acute decrease in BP has not been observed with LCI699 in healthy volunteers (up to 200 mg) or hypertensive patients (range tested = 0.25 mg - 2 mg/day). Doses used in this study will be higher than those where a BP effect was observed, and may therefore elicit larger decreases in BP than observed to-date. Patients with Cushing's disease have a high prevalence of hypertension and effective treatment of hypercortisolism may result in reductions in blood pressure.

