Some patients who enter this study may wash out current drug therapies in order to participate in this trial. It is to be expected that patients willing to consider washout of current therapies are those who are not responding to or tolerating their current therapies, and for whom the risk of a relatively short washout may be considered acceptable to test whether another therapy works better. There is a theoretical risk that if current effective therapy would be withdrawn, that cortisol levels would increase, and that patients would not respond well to LCI699. However, preliminary data from this PoC study indicate that all patients analyzed responded to LCI699. There is a risk that some patients may lose UFC control over time (“therapeutic escape”) while participating in the longer treatment evaluation. If a patient is not responding

to, or not tolerating an effective dose of, LCI699, they can be withdrawn from the study and resume their prior therapy.

Potential impact of delaying therapy

Some patients who enter this study may have a new diagnosis of Cushing's disease. The standard of care therapy for Cushing's disease is surgical resection of the ACTH producing tumor.

Entry into this study may delay the time to the provision of standard effective therapy. If LCI699 is effective, initiation of medical therapy to reduce excess cortisol may improve patient symptoms and improve medical co-morbidities which can improve their ability to tolerate the surgery. If LCI699 is not effective, the patient may experience extra weeks of excess cortisol exposure. If a patient is not responding to, or not tolerating an effective dose of, LCI699 they can be withdrawn from the study and undergo surgical resection.

The standard of care therapy for Cushing's disease is surgical resection of the ACTH producing tumor. Cushing's disease patients enrolled under [Amendment 4](#) should have either failed standard therapy (including surgery) or can be de novo patients for whom surgery is not an option.

Preliminary data from this PoC study demonstrated that LCI699 is an effective medical therapy to reduce hypercortisolism. If a patient is not responding to, or not tolerating an effective dose of, LCI699 they can be withdrawn from the study ([Section 5.5.9](#)).

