5.5.4 Permitted dose adjustments and interruptions of study treatment

LCI699 dose will be titrated as outlined in [Section 3.1](#) or until normalization of UFC (below upper limit of normal, as per local lab levels). For patients who are unable to tolerate the protocol-specified dose scheme, dose adjustments are permitted. The following guidelines should be followed:

- If the patient has not reached normalization of UFC, but does not tolerate the current dose, administration of an intermediate dose between the current (untolerated) and preceding (tolerated) dose or repeated administration of the preceding, tolerated dose should be considered.
- If the patient has reached normalization of their UFC, but the current dose is no longer tolerated, an intermediate dose between the current dose and previous dose should be considered.
- If the patient had reached normalization of their UFC, but the current dose is no longer efficacious based on on-going UFC measurements, dose escalation should resume.
- If the patient has low serum cortisol or $UFC < LLN$, and the patient has signs/symptoms of adrenal insufficiency, a dose reduction of LCI699 should be considered.

These changes must be recorded on the Dosage Administration Record eCRF.

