5.5.7 Rescue medication

As this is the first study to evaluate LCI699 for Cushing’s disease there are no established rescue medications. If patients are not responding to, or not tolerating LCI699, they should be withdrawn from the study and other accepted therapies (surgical resection or other medications) should be initiated.

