9.5.2 Escape analysis

Only patients who attained UFC normalization during the study will be included in the escape analysis, where escape is defined as the loss of UFC control (i.e. UFC > ULN) on at least 2 consecutive visits at the highest tolerated dose after previously attaining UFC normalization. “First-time escape” is used to describe the first occurrence of 2 consecutive visits with uncontrolled UFC at the patient’s highest tolerated dose after attaining UFC normalization. Time to escape is defined as the number of weeks from the visit of first UFC normalization (mUFC \leq 1x ULN) to the first visit of first-time escape. For patients who have no safety issue, 30 mg bid is the highest tolerated dose. For patients who have dose reduction due to safety reasons, the resulting reduced dose will be the highest tolerated dose. For patients who discontinue the study due to AEs, the dosage at discontinuation will be considered the highest tolerated dose. For all other situations, patients will be considered as not reaching their highest tolerated dose.

The median time to escape and corresponding 95% confidence interval will be calculated using Kaplan-Meier methodology for each cohort. The Kaplan-Meier curves will be presented. In this analysis, a patient who never had two consecutive visits with uncontrolled UFC at his/her highest tolerated dose will be censored at his/her last visit with mUFC assessment.

In addition, time to escape will be summarized using descriptive statistics by cohort for patients who meet escape criteria.

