### 7.3.2.4 Escape analysis

Only patient who attained UFC normalization during the study will be included in this analysis, where escape is defined as the loss of UFC control (i.e. UFC  $>$  ULN) on at least 2 consecutive visits at the highest tolerated dose after previously attaining UFC normalization. "First-time escape" is used to describe the first occurrence of 2 consecutive visits with uncontrolled UFC at the patient's highest tolerated dose after attaining UFC normalization. Time to escape is defined as the number of weeks from the visit of first UFC normalization (mUFC  $\leq 1 \times$  ULN) to the first visit of first-time escape. The definition for "highest tolerable dose" of LCI699 is provided in this paragraph. For patients who have no safety issue, 30 mg bid is the highest

tolerated dose. For patients who have dose reduction(s) because of an intolerable adverse event, the highest tolerated dose is the highest dose at which no AE requiring dose reduction is reported. For patients who discontinue the study due to AE, the highest tolerated dose is the highest prior dose at which no intolerable AE was reported. For all other situations (i.e., LCI699 dose is < 30mg bid, and there has been no AE leading to dose reduction or study drug discontinuation reported at the effective treatment dose), patients will be considered as not reaching their highest tolerated dose.

The median time to escape and corresponding two-sided 95% confidence interval will be calculated using Kaplan-Meier methodology for each cohort. The Kaplan-Meier curves will be presented. In this analysis, a patient who never had two consecutive visits with uncontrolled UFC at his/her highest tolerated dose will be censored at his/her last visit with mUFC assessment. In addition, time to escape will be summarized using descriptive statistics by cohort for patients who meet escape criteria.

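### The escape curve censors patients who stop LCI699 for lost UFC control after one uncontrolled visit, and no sensitivity analysis tests this

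*SAP*

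**What the plan says.** SAP 7.3.2.4 and protocol 9.5.2 restrict the escape analysis to patients who reached normal UFC. Escape is UFC above ULN at two or more consecutive visits at the highest tolerated dose. In the SAP, anyone without a consecutive pair of visits "with uncontrolled UFC at his/her highest tolerated dose will be censored at his/her last visit with mUFC assessment". The protocol has the same rule: such a patient "will be censored at his/her last visit with mUFC assessment". Neither text asks why the patient left. The only other escape output is a descriptive summary of patients who met the criteria.

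The two-visit requirement is deliberate. The Amendment 5 rationale (modified definition of escape) states: "The requirement of uncontrolled UFC on two consecutive visits is intended to ensure that the elevated UFC is not due to lab error", and gives small excursions above ULN as a second reason.

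The protocol describes what happens when control is lost:

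- Section 5.5.4: if a patient had normalised "but the current dose is no longer efficacious based on on-going UFC measurements, dose escalation should resume".
- Section 3.5, potential benefits: "Patients will be discontinued from LCI699 treatment in case of unsatisfactory response".
- Section 3.5, impact of discontinuing therapy: directly after raising therapeutic escape, it says of patients who do not respond or do not tolerate an effective dose that "they can be withdrawn from the study and resume their prior therapy".
- Section 5.5.7: "If patients are not responding to, or not tolerating LCI699, they should be withdrawn from the study".

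Protocol 3.1 sets visits "every 3 months during the first 18 months of extension-2", then every 6 months. SAP Table 8-2 puts the last 3-month visit (Visit 26) at Month 34 and Visit 27 at Month 40.

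**The concern.** Kaplan-Meier estimation assumes that a censored patient has the same future risk of the event as those still followed. A patient who stops because UFC control was lost does not: the reason for leaving is nearly the event itself. Censoring that patient at the last mUFC visit removes a probable escape from the numerator and can bias the escape-free curve upward.

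The response-rate analysis treats early discontinuation the opposite way. SAP 7.3.2.1 counts early discontinued patients as non-responders at all later time points, administrative exits apart. The supportive analysis there covers response rate only, so nothing planned shows how far the escape curve depends on its censoring rule.

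Escape is a secondary objective kept for the Final CSR (SAP 3.2), and sustained control was a stated reason for the longer treatment added by Amendment 4 (protocol 3.2). The curve would be read as evidence of durability.

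**Working it through.** The plan states no event count, power or precision for the escape analysis, so there is no figure of its own to reproduce. Three things can be checked.

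**1. Can the End of Treatment visit supply the second uncontrolled value?** Protocol section 6 asks for this visit promptly after stopping, and the schedule includes UFC. SAP 8.3 maps it to the next scheduled visit only if it falls between (gap ÷ 2) and (gap + next gap ÷ 2) days after the last scheduled visit. The SAP's own example is Visit 6 with 14-day gaps: 14/2 = 7 and 14 + 14/2 = 21 days, which reproduces. With equal successive gaps:

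| Visit gap | Earliest mapped day | Latest mapped day |
|---|---|---|
| 28 days | 14 | 42 |
| 84 days | 42 | 126 |
| 3 months (91.3 days) | 45.7 | 137 |
| 6 months (182.6 days) | 91.3 | 273.9 |

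A prompt End of Treatment visit in late extension-2, within about 91 days of the last visit, therefore becomes an unscheduled visit attached to that last visit. SAP 8.3 also allows off-schedule laboratory values to appear in listings only. SAP 8.4 needs two specimens for a valid mUFC, and the extensions collect only two. SAP 7.3.2.4 does not say whether an unscheduled End of Treatment mUFC counts.

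**2. When do the 6-month visits apply?** All 17 core completers had finished 154 days by 1 March 2014 (Amendment 6 status). The latest first dose was therefore about 28 September 2013, give or take the 2-day window. Adding 34 months gives about 28 July 2016. After that, every ongoing patient is on 6-month visits.

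**3. How far could the curve move?** The amendment status paragraphs give patients ongoing: 16 in extension-1 (1 March 2014), 12 (30 November 2015), 11 (14 June 2017) and 10 (3 May 2018). That is 4, 1 and 1 exits. The four are set aside because their window includes the optional move into extension-2. For the other two, assume that:

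- every patient had normalised;
- there were no other escapes;
- the highest tolerated dose had been reached;
- calendar risk sets stand in for weeks since normalisation.

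| Exits that were for lost control | Planned curve | Such exits counted as escape |
|---|---|---|
| Neither | 100% | 100% |
| Only the exit from 12 | 100% | 11/12 = 91.7% |
| Only the exit from 11 | 100% | 10/11 = 90.9% |
| Both | 100% | 11/12 × 10/11 = 83.3% |
| One later exit from 10 (hypothetical, alone) | 100% | 9/10 = 90.0% |

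The exit after 14 June 2017, and any later one, falls under 6-month visits.

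Curves are also drawn per cohort. Of the 19 patients enrolled under Amendment 4, SAP section 6 puts 15 in the expansion cohort, which leaves 19 − 15 = 4 in the follow-up cohort (an inference). One reclassified exit gives at most 3/4 = 75% in the follow-up cohort and at most 14/15 = 93.3% in the expansion cohort.

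**The case against.** The strongest reply is that the path is narrow. The patient must normalise, lose control while already at the highest tolerated dose, and be stopped after a single uncontrolled visit. The prescribed first step is renewed escalation, and no section tells sites to stop after one visit. The documents attribute no exit to lost control; the one exit reason they give is an adverse event (Amendment 5 status). This stands, and it is why the number affected may be zero. But a patient at 30 mg bid or at a tolerability limit cannot escalate, and the timing of stopping is left to the investigator.

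The second reply is that a further measurement is already planned. UFC is collected at End of Treatment, and the escape definition speaks of visits, not scheduled visits. A programmer could count it, but another reading SAP 8.3 could leave it out, so the event count depends on an unstated choice. Local UFC values may be captured between visits (protocol 6.5), but no rule brings them into the escape definition.

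The third reply is that the information appears elsewhere: disposition gives reasons for discontinuation in the extension, laboratory values are listed, and the response rate counts early discontinuers as failures. With 19 patients, a reader could identify the cases by hand. That reduces the harm, but the curve itself would still be shown without any test of its censoring. The study is exploratory and single-arm, so no hypothesis test is affected.

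**Conclusion.** The concern holds. The stated rule allows informative censoring of patients who stop for lost response, and no escape sensitivity analysis is planned. The direction of any bias is towards a more favourable curve; its size is unknown. Under the assumptions listed, one or both of the two exits would bring the curve to between 83% and 92%, against 100% as planned. A single case could cost the follow-up cohort's curve 25 points or more if that cohort has 4 patients. The median time to escape and the response rates are unlikely to change. This is a worthwhile correction to a secondary, descriptive analysis and does not undermine the trial's main results.

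**What to change.** Keep the two-visit definition as the primary analysis and add the following to SAP 7.3.2.4:

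1. One sensitivity Kaplan-Meier analysis. A normalised patient who stops LCI699 for lack or loss of UFC response, with the last on-treatment mUFC above ULN at the highest tolerated dose, counts as an escape at the first visit of that uncontrolled run.
2. One sentence stating that an End of Treatment mUFC from urine collected on drug can be the second consecutive visit, regardless of the SAP 8.3 window.
3. If the highest-tolerated-dose condition is also relaxed, for example for a patient stopped below 30 mg bid with no dose-limiting adverse event, a separate version labelled treatment failure.

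The drawback is that one value just above ULN can count as an escape in the sensitivity analysis, so it must not replace the primary rule. The cost is one extra analysis and one clarifying sentence. Discontinuation reasons and mUFC are already collected, so no protocol change, visits or samples are needed. If nobody is affected, the primary and sensitivity curves coincide and the durability claim is stronger.

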## **7.4 Pharmacokinetic evaluation**

No pharmacokinetic assessments were performed after Week 22, and the pharmacokinetic results have been reported in previous CSRS. No PK analyses will be included in the Final CSR.

